4.5 Study Intervention

EMBr Wave devices will be worn by study participants during the daytime and nighttime during the treatment periods of the trial. Participants will be asked to use the device as needed during the daytime and nighttime for management of hot flashes and night sweats. Participants will be asked to complete the hot flash assessments described above. Because hot flashes are transient and the EMBr Wave device is not expected to modify the underlying condition, a carry-over effect is unlikely in the crossover design. Due to the unlikelihood of carry-over and to avoid unnecessarily increasing patient burden, we will not use a wash-out period.

4.6 Clinical Assessment

Participants will be evaluated for hot flashes prior to initiation of the study. For participants enrolled to the study, the study team will abstract from the electronic medical record: clinical characteristics (cancer type, stage, receptor status), treatment history (surgery, radiation therapy, chemotherapy, endocrine therapy) and associated dates, and medications that affect or treat hot flashes. Chart abstraction will include the use of antidepressant medications since these drugs may have an effect on hot flashes.

4.7 Duration of Therapy

In the absence of treatment delays due to adverse event(s), treatment may continue until one of the following criteria applies:

- Intercurrent illness that prevents further administration of treatment,
- Unacceptable adverse event(s),
- Patient decides to withdraw from the study, or
- General or specific changes in the patient's condition render the patient unacceptable for further treatment in the judgment of the investigator
- Loss of device greater than one time

[Type here]

4.8 Duration of Follow up

Patients will not be followed after eight weeks. Patients removed from study for unacceptable adverse event(s) will be followed until resolution or stabilization of the adverse event.

4.9 Criteria for Removal from Study

The following criteria will be used for removal of patients from the study: (1) patient withdraws their participation; (2) patient has a disease progression or dies (whichever occurs first); (3) the study is terminated by the Principal Investigator; The reason for study removal and the date the patient is removed must be documented in the Case Report Form.

4.10 Adherence

Because of the limited anticipated adverse effects from the device and the ease of wearing the device, we anticipate excellent adherence. Device usage will be electronically tracked through the study. Lost devices will be replaced once and if recurred, will be removed from study.

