The HFRDIS, Daily Hot Flash Score, and OCEAN survey will be administered on paper or virtually via RedCap survey distribution at baseline. Participants will be given paper Daily Hot Flash Score sheets for their own use. For study data collection, electronic surveys will be sent by email via Research Electronic Data Capture (REDCap) for daily and weekly hot flash assessments and the post-treatment satisfaction and efficacy questionnaires. Survey reminder emails and phone calls from study team will be sent to participants for incomplete HFRDIS surveys and satisfaction and efficacy assessments. If a participant initiated the daily surveys on paper prior to the study team using electronic data collection, she will continue using paper assessments for the duration of the study. If assessments are incomplete at end of intervention, the study coordinator will utilize paper forms to collect assessments, as appropriate.

Virtual enrollment will be presented as an option to eligible participants. In this option, calls (phone and/or video) will be done between the research coordinator and participant to discuss the study; screen for eligibility; discuss the informed consent and how to sign it; orient the patient to the device and associated smart phone application; and discuss how to return the device at the conclusion of the device usage. The informed consent document will be sent to the participant to sign via email or mail to obtain a pen signature after the participant has verbally agreed to participate in the study during the call. In addition to either receiving the signed informed consent form via email or mail, the participant will also be able to email the full picture of their signed informed consent form to the study coordinator's email and this will serve as a third option of informed consent documentation. After the consent document is signed, randomization will be done and the research coordinator will then inform the patient the

[Type here]

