5.0 POTENTIAL TOXICITY, DOSE MODIFICATIONS, AND MANAGEMENT

Because EMBr Wave is a superficial, non-invasive device, we expect to see very little or no toxicities at all that are seen in its chronic use. Regardless, we will monitor for them. The severity of adverse reactions is categorized from grade 1 to grade 5 in increasing severity.

Table 4. General descriptors for the toxicity grades, ranged from mild to fatal.

Grade 1	Mild – the adverse reaction does not interfere in a significant manner with the subject’s normal functioning level. It may be an annoyance.
Grade 2	Moderate – the adverse reaction produces some impairment of functioning but is not hazardous to health. It is uncomfortable and/or an embarrassment
Grade 3	Severe – the adverse reaction produces significant impairment of functioning or incapacitation and is a definite hazard to the subject’s health
Grade 4	Severe – adverse reactions that include or lead to either a) a life-threatening event, though acute and without permanent effect, b) prolonged inability to resume usual life pattern, or c) impairment of ability to adequately deal with future medical problems
Grade 5	Death related to AE

Toxicity will be monitored during study visits and telephone calls using the National Cancer Institute Common Terminology Criteria for Adverse Events version 5.0 (CTCAE) of the National Cancer Institute will be used:

[Type here]

(https://ctep.cancer.gov/protocoldevelopment/electronic_applications/docs/CTCAE_v5_Quick_Reference_5x7.pdf). Grade 3, 4 and 5 toxicities that are related to the study will be reported as adverse events.

Patients with Grade 3-4 adverse reactions that are related to the study will be removed from the study.

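### Two device-related events take a woman off the study rather than only off the device, so a Group A woman can lose her whole no-device month; the effect on the secondary efficacy estimate is small and cheap to avoid

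*Combined protocol and SAP*

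**What the plan says.** Five sections of the combined protocol and SAP bear on what happens when a woman can no longer use the device.

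- **4.10 Adherence:** "Lost devices will be replaced once and if recurred, will be removed from study".
- **5.0 Potential Toxicity:** "Patients with Grade 3-4 adverse reactions that are related to the study will be removed from the study".
- **4.7 Duration of Therapy** lists "Loss of device greater than one time", and also unacceptable adverse events, among the reasons for ending treatment.
- **4.9 Criteria for Removal from Study** opens with "The following criteria will be used for removal of patients from the study" and then names patient withdrawal, progression or death, and termination of the study. Neither device loss nor an adverse reaction appears.
- **4.8 Duration of Follow up** caps follow-up at eight weeks and adds: "Patients removed from study for unacceptable adverse event(s) will be followed until resolution or stabilization of the adverse event". It does not mention efficacy surveys.

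On data collection, section 4.4 states that "electronic surveys will be sent by email via Research Electronic Data Capture (REDCap) for daily and weekly hot flash assessments", and adds: "If assessments are incomplete at end of intervention, the study coordinator will utilize paper forms to collect assessments, as appropriate". The calendar in 7.2 schedules HFRDIS weekly and the daily score every day to Day 56 in both groups. Neither place says what applies to a removed woman.

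Section 12.1 declares all analyses intent-to-treat. It keeps available observations in the mixed model, compares leavers with completers, and assesses the impact of loss by multiple imputation. For compliance, leavers count as not wearing the device.

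**The concern.** Both removal triggers arise from using the device, so they fall in the device month, and that month comes at different times in the two sequences. Group A wears the device on Days 1-28 and has its no-device month afterwards. Group B has the no-device month first. If removal ends the surveys, a removal costs Group A the control half of the within-woman comparison and leaves Group B's untouched.

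The model then has to fill the gap by assuming that the removed woman's unseen scores behave like those of comparable women who stayed. Women who react badly to the device, or stop using it, may benefit less than average. If so, their weight in the treatment contrast falls and the estimated benefit rises. What is at stake is the preliminary efficacy estimate, which the secondary objectives want as an effect size for powering a Phase III trial.

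**Working it through.** **1. What is lost, from the calendar in 7.2**

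| Woman removed during her device month | No-device HFRDIS kept | No-device daily scores kept |
|---|---|---|
| Group A (Days 1-28) | 0 of 4 | 0 of 28 |
| Group B (Days 29-56) | 4 of 4 | 28 of 28 |

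**2. Inputs for sizing the effect**

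- From the documents: 50 women, 25 per sequence (1.1); four weekly HFRDIS per period (7.2); the mixed model of 12.1 with treatment, sum-to-zero period, their interaction, and random subject and subject-by-treatment effects. The plan gives no figure for this issue. Its power example, an effect of 0.7 in within-subject SD units, serves only as a scale.
- Assumed: SDs of 1.5 (subject), 0.7 (individual treatment effect) and 1 (error); the woman stops after two device weeks; she has no benefit once off the device. The last follows the protocol's reasoning in 4.5: "Because hot flashes are transient and the EMBr Wave device is not expected to modify the underlying condition". The documents give no removal rate, so one and three removals are shown.

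**3. Method**

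Let T be the average effect in the women who are not removed. Generalised least squares on the 12.1 model gives the expected treatment estimate under three kinds of data collection:

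- *Full follow-up, intent-to-treat:* every survey is collected to Day 56.
- *While on device:* off-device weeks of the device month are dropped and the no-device month is kept.
- *Removed:* nothing is collected after removal.

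The full follow-up value can be checked by hand. With complete data it is the mean of the two groups' device-month effects. One no-benefit woman gives (24/25 + 1)/2 = 0.980T. Three give (22/25 + 1)/2 = 0.940T. Three with full benefit for half the month give ((22 + 1.5)/25 + 1)/2 = 0.970T.

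**4. Results**

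| Removed women | Full follow-up | While on device | Removed | Removed vs full follow-up | Removed vs while on device |
|---|---|---|---|---|---|
| 1, no benefit, A | 0.980T | 0.984T | 0.9954T | +1.6% | +1.2% |
| 1, no benefit, B | 0.980T | 0.984T | 0.984T | +0.4% | 0% |
| 3, no benefit, all A | 0.940T | 0.951T | 0.986T | +4.9% | +3.7% |
| 3, no benefit, all B | 0.940T | 0.951T | 0.951T | +1.2% | 0% |
| 3, half benefit, all A | 0.955T | 0.976T | 0.993T | +4.0% | +1.8% |
| 3, half benefit, all B | 0.955T | 0.976T | 0.976T | +2.15% | 0% |
| 3, full benefit, either group | 0.970T | 1.000T | 1.000T | +3.1% | 0% |

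**5. In standard errors**

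The standard error with full follow-up is 0.141 error SDs. At T = 0.7:

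- one no-benefit woman, Group A: 0.7 × (0.9954 − 0.980)/0.141 = 0.08
- one no-benefit woman, Group B: 0.7 × (0.984 − 0.980)/0.141 = 0.02
- three no-benefit women, all Group A: 0.7 × (0.986 − 0.940)/0.141 = 0.23

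The cost in precision is also small. With three removals the standard error rises by 2.8% (all A) or 0.6% (all B) over full follow-up.

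**6. Sensitivity, three no-benefit women against full follow-up**

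With subject SD from 0.5 to 2.0 and individual-effect SD from 0.3 to 1.0, the inflation is 1.7% to 5.9% (all A) and 0.8% to 2.1% (all B). Stopping after device week 1 or 3 gives 0.5% to 5.1% across the two groups.

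**7. Reach**

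Section 1.1 reports 23 women enrolled and none active at the amendment, leaving 50 − 23 = 27. At roughly equal allocation, 13 to 14 of these are in Group A. Three Group A removals would therefore be about 3/13.5 = 22% of them.

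**The case against.** The strongest objection is to the premise. No section says that surveys end. Section 4.9, which exists to list removal criteria, names neither trigger. Section 4.7 can be read as stopping treatment only. The sentence in 4.10 is garbled, since its grammatical subject is the device. The adverse-event sentence in 4.8 may simply extend follow-up past eight weeks. What is certain is that four sections do not line up. This stands, and it is why the lost month is stated here as a consequence of one reading, though the ordinary one.

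Second, section 12.1 already deals with missing efficacy data. That is true of the analysis, but the mixed model and imputation cannot recover a within-woman contrast that was never observed. A reader might infer that the intent-to-treat declaration is violated. It is not: every randomised woman stays in the analysis with the data she gave, and the weakness is in collection.

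Third, the three-removal case has no basis in the documents. Section 5.0 expects very little toxicity, 4.10 expects excellent adherence, and removal for loss needs two losses within 28 days. This stands; one removal is the more realistic case.

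Fourth, part of the gap is a choice of estimand. Against a while-on-device estimate it is zero for Group B and for women with average benefit. What remains is confined to Group A and needs removed women to benefit less than average, which nothing in the documents supports for device loss. This also stands.

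**Conclusion.** The point holds as a small, cheap improvement to a secondary estimate. Sections 4.10 and 5.0 state removal from the study, 4.7 and 4.9 do not match them, and no section continues the efficacy surveys afterwards. On the ordinary reading, the loss falls on Group A's no-device month and spares Group B's.

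The realistic size is one removal, an inflation of 0.4% to 1.6%. The 4.9% case is an unlikely upper bound under the base assumptions. All of these figures rest on assumed SDs, an assumed stopping time and assumed numbers of removals. The part that does not depend on the choice of estimand is the lost Group A no-device month.

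A reader might infer that the efficacy result is materially biased or that the feasibility conclusion is at risk. Neither follows. The shift is a small fraction of a standard error even in the worst base case, and the compliance endpoint is protected because leavers are recorded as not wearing the device.

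**What to change.** Make a second device loss and a related Grade 3-4 reaction reasons to stop the device, not to leave the study, and align 4.9, 4.10 and 5.0 with 4.7. Add one sentence: after the device is stopped, the emailed HFRDIS and daily score surveys continue to Day 56 unless the woman withdraws consent or declines. Use these data in the intent-to-treat model. Report as a sensitivity analysis a while-on-device estimate that drops off-device weeks of the device month and keeps the no-device month. Keep the mixed model and multiple imputation of 12.1 for whatever is still missing.

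The cost is wording in three sections plus that sentence. No visits are added, because the surveys already go out by email. Three downsides should be accepted openly:

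- A woman no longer using the device, possibly after a Grade 3-4 reaction, is asked for the remaining surveys: in Group A up to 28 daily scores and 4 HFRDIS in the no-device month, and in either group the rest of the device month. Hence the option to decline.
- Off-device weeks slightly dilute the intent-to-treat estimate (0.970T for three full-benefit women), which is why the sensitivity analysis is needed.
- The change reaches only the 27 or so women not enrolled at the amendment dated 1/5/2022.

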5.0 POTENTIAL TOXICITY, DOSE MODIFICATIONS, AND MANAGEMENT

Because EMBr Wave is a superficial, non-invasive device, we expect to see very little or no toxicities at all that are seen in its chronic use. Regardless, we will monitor for them. The severity of adverse reactions is categorized from grade 1 to grade 5 in increasing severity.

Table 4. General descriptors for the toxicity grades, ranged from mild to fatal.

Grade 1	Mild – the adverse reaction does not interfere in a significant manner with the subject’s normal functioning level. It may be an annoyance.
Grade 2	Moderate – the adverse reaction produces some impairment of functioning but is not hazardous to health. It is uncomfortable and/or an embarrassment
Grade 3	Severe – the adverse reaction produces significant impairment of functioning or incapacitation and is a definite hazard to the subject’s health
Grade 4	Severe – adverse reactions that include or lead to either a) a life-threatening event, though acute and without permanent effect, b) prolonged inability to resume usual life pattern, or c) impairment of ability to adequately deal with future medical problems
Grade 5	Death related to AE

Toxicity will be monitored during study visits and telephone calls using the National Cancer Institute Common Terminology Criteria for Adverse Events version 5.0 (CTCAE) of the National Cancer Institute will be used:

[Type here]

(https://ctep.cancer.gov/protocoldevelopment/electronic_applications/docs/CTCAE_v5_Quick_Reference_5x7.pdf). Grade 3, 4 and 5 toxicities that are related to the study will be reported as adverse events.

Patients with Grade 3-4 adverse reactions that are related to the study will be removed from the study.

7.0 TREATMENT PLAN

7.1 Treatment Plan and Overview

Eligible patients will be approached by study personnel in the clinics at Stefanie Spielman Comprehensive Breast Center, the James Cancer Hospital, and the Center for Women's Health at the Ohio State University Wexner Medical Center. The person obtaining informed consent will tell the patient that 1) participation is voluntary, 2) participation or non-participation will not affect their usual care and management, and 3) patient confidentiality will be maintained in the event that the results of the study are published. The potential toxicities associated with EMBr Wave will be explained fully to the patient. Patients will be provided with a consent form to review, and all questions will be answered. After the signed informed consent has been obtained, a study identification number will be assigned to the patient for use on all data collection forms and samples. Medications and supplements will be reviewed with participants. Research team members may periodically call participants on the phone to remind them to complete the study surveys and to see if the participants are having any problems with the watch.

7.2 Study Calendar

Informed consent, randomization		
	Group A	Group B
Day 0	
• Receive EMBr Wave• EMBr Wave orientation with introduction to device and mobile application• HFRDIS questionnaire• Daily Hot Flash Score• OCEAN psychographic survey	
• HFRDIS questionnaire• Daily Hot Flash Score• OCEAN psychographic survey
Days 1–28	
• Daily Hot Flash Score• Device usage assessment	
• Daily Hot Flash Score
Days 7, 14, 21, 28	
• HFRDIS questionnaire	
• HFRDIS questionnaire
Day 28	
• Return EMBr Wave• Patient satisfaction / perceived efficacy assessment	
• Receive EMBr Wave• EMBr Wave orientation with introduction to device and mobile application
Days 29–56	
• Daily Hot Flash Score	
• Daily Hot Flash Score• Device usage assessment
Days 35, 42, 49, 56	
• HFRDIS questionnaire	
• HFRDIS questionnaire
Day 56		
• Return EMBr Wave

[Type here]

		
• Patient satisfaction / perceived efficacy assessment
--	--	--

In addition, patients will record their Daily Hot Flash Score daily in their journals.

9.0 ADVERSE EVENT REPORTING

Adverse event: Any unfavorable and unintended sign (including abnormal laboratory finding), symptom, or disease temporally associated with the use of a medical treatment or procedure, regardless of whether it is considered related to the medical treatment or procedure; also an “unanticipated problem” of any nature (e.g., psychological or social harm) (designated as unrelated, definitely related, probably related, or possibly related; see below)

Serious adverse event: Any adverse event that is fatal or life threatening, is permanently disabling, requires inpatient hospitalization or prolongs hospitalization, or results in a congenital anomaly or birth defect.

Life-threatening event: Any adverse event in which the subject is at immediate risk of death from the reaction as it occurs; does not include a reaction that, if it were to occur in a more serious form, might cause death

Unexpected event: Any adverse event that is not identified in nature, severity, or frequency in the investigator brochure, study protocol, consent form, or IND application; or the event was more serious than anticipated.

9.1 Attribution of the Adverse Events

Definite: AE is CLEARLY RELATED to the study treatment.

Probable: AE is LIKELY RELATED to the study treatment.

Possible: AE MAY BE RELATED to the study treatment.

Unlikely: AE is DOUBTFULLY RELATED to the study treatment.

Unrelated: AE is CLEARLY NOT related to the study treatment

9.2 Documentation

CTCAE version 5.0 will be utilized for AE reporting. All appropriate treatment areas should have access to a copy of the CTCAE version 5.0. A copy of the CTCAE version 5.0 can be downloaded from the CTEP web site

http://ctep.cancer.gov/protocolDevelopment/electronic_applications/ctc.htm.

For expedited reporting purposes only:

- AEs for the agent that are bold and italicized in the CAEPR (i.e., those listed in the SPEER column, Section 7.1.1) should be reported through CTEP-AERS only if the grade is above the grade provided in the SPEER.

All adverse events must be documented in detail within the medical record. The patient will be observed and monitored carefully until the condition resolves, stabilizes, or its cause is identified. All adverse events, including laboratory abnormalities, will be followed up according to good medical practices. Information to be recorded includes the following:

[Type here]

1. Specific type of reaction.
2. Duration of reaction.
3. Severity/grade of reaction according to the NCI Common Terminology Criteria for Adverse Events v5.0 (CTCAE).
4. Suspected cause of the reaction (i.e. possibly or probably related to one of the following: study intervention, progression of disease, concurrent medications, concurrent illness, or other factors).
5. Patient's response to medical interventions.

9.3 Reporting

Since it is difficult to discern which AEs may impact gait and balance testing, all AEs will be collected, not just neuropathy symptoms. Although unlikely, some unrelated symptoms may impact gait and balance and may also be indirectly related to neuropathy symptoms (e.g. cytopenias and fatigue may impact balance and gait).

10.0 CRITERIA FOR RESPONSE ASSESSMENT

All patients will be considered evaluable. Participants with only baseline measures will be considered as drop-outs.

10.1 Measurement of Effect

We will evaluate effect of EMBr Wave by PRO, primarily HFRDIS. We will also include satisfaction/perceived efficacy questions measuring ratings on a 10-point Likert scale with 10 being most satisfied or most effective.

